3.3. Concomitant Care

Participants will receive the following care while taking trial medication.

- a) Surgery: The participant and surgeon will determine the type of operation. This management is not randomly assigned and is determined by injury characteristics. The operation can be performed before or after randomization; randomization must occur within 10 days of injury.
- b) Medications: Analgesia can be provided by acetaminophen, opioids, and/or nonsteroidal anti-inflammatory drugs (NSAID) as required. The NSAIDs may have a confounding effect on the ROM measures by preventing HO following elbow injuries. Heterotopic ossification (HO) refers to bone formation in soft tissue. NSAIDs may be used in this trial as an analgesic at the discretion of the participant and surgeon because of the known analgesic benefits for

musculoskeletal injury and the ubiquitous accessibility to NSAIDs with non-prescription preparations.

lberta Health

c) Rehabilitation/Splints: If possible, at the site, a physiotherapist will direct a standardized home exercise program (HEP) for all groups. The HEP will consist of active ROM exercises for elbow extension-flexion arc and forearm pronation-supination arc performed 3x/day with 20 repetitions. Visits to the physiotherapist every 2 weeks will monitor progress and reinforce adherence to home therapy. Stretching splints will be used when physiotherapy alone is insufficient, which occurs at least 12 weeks post-randomization.

4. Sample Size Determination

The sample size was estimated using the Analysis of Covariance (ANCOVA) model using the mean difference of injured and contralateral elbow extension-flexion arc ROM at Week 12. The sample size was calculated based on a mean difference of 15° in the extension-flexion range of motion and a standard deviation of 45° between participants who received 2 mg or 5 mg Ketotifen Fumarate and those who received a placebo, using 95% power and a two-sided test at the 0.05 α -level. The sample size was recalculated due to COVID-19 (which temporarily impacted enrolment) and budgetary constraints. A total sample size of 381 participants (127 participants per arm) was determined to be adequate based on a mean change of 10° extension-flexion arc ROM from baseline to week 12 and a standard deviation of 25°, assuming an overall dropout rate of 11%. The standard deviation used was obtained from PERK-1 trial data. Following permission from Health Canada, the sample size was increased to 395.

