| Study Objectives | Endpoints |
|------------------|---|
| | i. The Disability of the Arm, Shoulder, and Hand |
| | (DASH) |
| | ii. The Pain Catastrophizing Scale (PCS)) |
| | iii. The Oxford Elbow Score (OES) |
| 5. Safety | The proportion of SUSAR up till week 12 |
| | The proportion of fatal or life-threatening SAE up till week 12 |
| | The proportion of other SAE up till week 12 |
| | The proportion of composite reoperation for all elbow-related causes at week 12 |
| | The proportion of participants requiring reoperation for contracture at week 12 |
| | The proportion of SUSAR up till week 52 |
| | The proportion of fatal or life-threatening SAE up till week 52 |
| | The proportion of other SAE up till week 52 |
| | The proportion of composite reoperation for all elbow-related causes at week 52 |
| | The proportion of participants requiring reoperation for contracture at week 52 |

6. Analysis Set

a) Intent-to-Treat (ITT) Population: The primary endpoint analysis will be conducted on the ITT population, which includes all study participants and the treatment group to which they were assigned (i.e., the intended treatment). An ITT analysis will also be conducted for the secondary endpoints.

Alberta Health

- b) **Per Protocol (PP) Population:** The PP population includes all participants randomized and treated, with no major protocol deviations, including not meeting inclusion/exclusion criteria, not receiving the planned dose, receiving the incorrect study drug, or not obtaining consent (i.e., as treated). The primary analysis will be repeated on the PP population.
- c) **Safety Population:** The safety population comprises all participants receiving any amount of study drug. Participants will be analyzed based on the intervention they receive.

7. Statistical Analysis

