7.1. Descriptive Analysis

Continuous endpoints will be summarized using means, standard deviation, medians, and interquartile ranges. The differences among groups will be compared using Kruskal-Wallis's test. Categorical endpoints will be summarized using frequency and proportion. Chi-square tests will be used to compare categorical endpoints. Point estimates with two-sided 95% confidence intervals will be produced for group differences. These endpoints, baseline covariate, and stratification factors used during randomization will be summarized by treatment intervention

for the ITT population. Similar analyses will be conducted for the PP population and safety population.

Alberta Health

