| from Week 2 to Week 52 | a) Analysis of Covariance (ANCOVA) This model will be used to assess the mean difference in OES score between Week 2 and Week 52 among the treatment groups after adjusting for OES score at Week 2 (baseline value). The model will have Dependent variable: The OES score at Week 52 Independent variable: Treatment group Covariate: OES score at Week 2, sex, age, side of injury is the same as the dominant hand, type of elbow injury, and concurrent injury will be regarded as fixed variables, and site as a random variable. Type of elbow injury is defined as AO/OTA classification, i.e., distal humerus vs. proximal radius and ulna. b) Mixed-effects linear regression model This model will be used to account for correlation among observations and estimate the effect of covariates on repeated outcomes. It will use the OES score recorded at the time points. Also, the baseline covariates sex, age, side of injury is the same as the dominant hand, type of elbow injury, and concurrent injury will be regarded as fixed variables, and site as a random variable. Type of elbow injury is defined as | Mixed-effect linear regression model: The mean difference and its corresponding 95% confidence intervals |
| | injury will be regarded as fixed variables, and site as a random variable. Type of elbow injury is defined as AO/OTA classification, i.e., distal humerus vs. proximal radius and ulna. | |

| Study Endpoint | Statistical Model | Estimate of treatment effects |
|---|---|--|
| | Safety | |
| Suspected unexpected Serious Adverse Reaction (SUSAR) up to Week 12 | The analyses will be unadjusted to avoid estimates with wide confidence intervals since we expected that the event rate might be low and that this is likely no event in some treatment groups. | Odds ratio and p-value for both the omnibus and pairwise differences models. |
| | Fisher's exact test The test will be used to compare the proportion of SUSAR up to Week 12 in the treatment groups. If the test produces a significant p-value at α = 0.05, a post-hoc test will be performed to identify groups that | |
| | differ. The p-values will be corrected using the Benjamin- Hochberg FDR method to ensure that the family-wise Type I error remains at 0.05. | |

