| Fatal or life-threatening SAE up to Week 12 | The analyses will be unadjusted to avoid estimates with wide confidence intervals since we expected that the event rate might be low and that this is likely no event in some treatment groups. | Odds ratio and p-value for both the omnibus and pairwise differences models. |
| | Fisher's exact test The test will compare the proportion of Fatal or life- threatening SAEs in the treatment groups up to Week 12. | |

| Study Endpoint | Statistical Model | Estimate of treatment effects |
|---|--|--|
| | If the test produces a significant p-value at α = 0.05, a post-hoc test will be performed to identify groups that differ. | |
| | The p-values will be corrected using the Benjamin- Hochberg FDR method to ensure that the family-wise Type I error remains at 0.05. | |
| Other Serious adverse effect (SAE) up to Week 12 | The analyses will be unadjusted to avoid estimates with wide confidence intervals since we expected that the event rate might be low and that this is likely no event in some treatment groups. | Odds ratio and p-value for both the omnibus and pairwise differences models. |
| | Fisher's exact test The test will compare the proportion of other SAE in the treatment groups up to Week 12. | |
| | If the test produces a significant p-value at α = 0.05, a post-hoc test will be performed to identify groups that differ. | |
| | The p-values will be corrected using the Benjamin- Hochberg FDR method to ensure that the family-wise Type I error remains at 0.05. | |
| Composite reoperation for all elbow-related causes at Week 12 | The analyses will be unadjusted to avoid estimates with wide confidence intervals since we expected that the event rate might be low and that this is likely no event in some treatment groups. | Odds ratio and p-value for both the omnibus and pairwise differences models. |
| | Fisher's exact test | |

| Study Endpoint | Statistical Model | Estimate of treatment effects |
|--------------------------------|---|---------------------------------|
| | The test will compare the proportion of composite reoperation for all elbow-related causes in the treatment groups at Week 12. If the test produces a significant p-value at α = 0.05, a post-hoc test will be performed to identify groups that differ. | |
| | The p-values will be corrected using the Benjamin- Hochberg FDR method to ensure that the family-wise Type I error remains at 0.05. | |

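### Table 2 asks for an omnibus odds ratio that a three-arm Fisher test cannot give, and makes the odds ratio the pairwise safety measure while expecting arms without events

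*SAP*

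**What the plan says.** Table 2 in SAP section 7.2 has ten safety rows: SUSAR, fatal or life-threatening SAE, other SAE, reoperation for any elbow-related cause, and reoperation for contracture, each at Week 12 and at Week 52. All ten carry the same estimate entry: "Odds ratio and p-value for both the omnibus and pairwise differences models".

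The named method is Fisher's exact test across the treatment groups. It is unadjusted, "since we expected that the event rate might be low and that this is likely no event in some treatment groups". The follow-up step reads: "If the test produces a significant p-value at α = 0.05, a post-hoc test will be performed to identify groups that differ". No safety row names a logistic or other odds-ratio model, a reference arm, or a convention for a pair in which one or both arms have no events.

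Section 7.1 adds a general rule: "Point estimates with two-sided 95% confidence intervals will be produced for group differences". It then extends this: "Similar analyses will be conducted for the PP population and safety population". It summarises categorical endpoints by frequency and proportion, but names neither the effect scale nor the interval method for them. Section 6 fixes the denominator: "The safety population comprises all participants receiving any amount of study drug".

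**The concern.** There are two problems with the estimate column.

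1. **Omnibus entry.** A table of three arms by event yes/no has two degrees of freedom. It contains two independent odds ratios, and no single number is its odds ratio. The cell cannot be completed as written.
2. **Pairwise entry.** The plan picks the odds ratio as effect measure for endpoints where it expects event-free arms. In that situation the odds ratio is 0, infinite or undefined. The expected sparseness is used only to justify leaving out covariates, not to choose a measure that copes with it.

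What is at stake is how safety differences are reported. If nothing is settled beforehand, the analyst decides with the data in hand whether to print infinity, apply a continuity correction or switch to another scale, and with which interval. These choices look very different on the page.

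**Working it through.** **Inputs.** Three arms, 1:1:1 (section 3.1). 127 per arm (section 4). Section 4 also says "the sample size was increased to 395", which is 395/3 ≈ 132 per arm and is used as a sensitivity check. Alpha is 0.05 (Table 2). The SAP gives no safety event rates, so any rate below is an assumption. Tables are written placebo/2 mg/5 mg.

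**1. The omnibus test carries no odds ratio.** The tables 0/2/7, 7/2/0 and 2/0/7 all give omnibus p = 0.0127 at 127 per arm. Their odds ratios against placebo (2 mg; 5 mg) are:

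- 0/2/7: infinity; infinity
- 7/2/0: (2/125)/(7/120) = 0.27; 0
- 2/0/7: 0; (7/120)/(2/125) = 3.65

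The p-value is the same and the directions differ, so the omnibus result does not correspond to any one odds ratio.

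**2. Which sparse tables reach omnibus significance?** With m events in total, a table a/b/c has probability C(127,a)·C(127,b)·C(127,c)/C(381,m). The exact p-value sums this over all tables no more probable than the observed one.

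- m = 3, most extreme table 0/0/3: 3 × (127·126·125)/(381·380·379) = 3 × 0.03645 = 0.109. Nothing with 3 or fewer events reaches 0.05.
- m = 4, table 0/0/4: 3 × (127·126·125·124)/(381·380·379·378) = 3 × 0.01196 = 0.036.

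Full enumeration gives these significant tables, up to the order of the arms:

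| Total events | Significant tables (p) |
|---|---|
| 4 | 0/0/4 (0.036) |
| 5 | 0/0/5 (0.012) |
| 6 | 0/0/6 (0.004) |
| 7 | 0/0/7 (0.001), 0/1/6 (0.019) |
| 8 | 0/0/8 (0.0004), 0/1/7 (0.007), 0/2/6 (0.031) |

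Each has at least one event-free arm. The first significant table with events in all three arms is 1/1/7, at 9 events (p = 0.023). The list is the same at 132 per arm.

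**3. How often does this arise?** Exact enumeration at 127 per arm with assumed rates:

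| Assumed rates | Omnibus significant | Significant and an event-free arm |
|---|---|---|
| 0.5% in all arms | 0.3% | 0.3% |
| 1% in all arms | 1.2% | 1.1% |
| 2% in all arms | 2.7% | 2.2% |
| 0.5/1/2% | 6.4% | 6.2% |
| 1/3/6% | 47% | 24% |
| 2/5/8% | 48% | 8% |
| 3/5/10% | 53% | 2% |

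The chance that at least one arm has no events, whatever the omnibus result, is 1 - [1 - (1 - p)^127]^3 at a common rate p. This is 90% at 0.5%, 63% at 1% and 21% at 2%.

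**4. What would be printed.** For 6 v 0 of 127:

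- Odds ratio: infinity, exact 95% interval 1.20 to infinity, Fisher p = 0.029. A 0.5 correction would print 13.6 instead.
- Risk difference: 6/127 = 4.7%, Newcombe 0.8% to 9.9%.

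For 0 v 0 the odds ratio is undefined. The Wald interval for the risk difference is 0 to 0. The Wilson upper limit for 0 of 127 is z²/(n + z²) = 3.84/130.84 = 2.9%, so Newcombe gives -2.9% to 2.9%.

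For 1 v 0, Wald gives -0.7% to 2.3% and Newcombe -2.2% to 4.3%.

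**The case against.** Several points on the other side are sound.

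- **The estimate column is unconditional.** A reader might infer that, when the omnibus test is not significant, the unfillable omnibus odds ratio is the only effect estimate Table 2 requests. The documents do not establish this. The condition in the rows governs a post-hoc test, and the SAP does not say whether pairwise odds ratios are withheld otherwise. If they are always reported, the loss of an estimate disappears, but pairs with an event-free arm become more frequent.
- **Section 7.1 already promises estimates with intervals in the safety population.** It would be wrong to say that the plan offers no effect estimate outside Table 2. For an endpoint summarised as a proportion, a difference in proportions is the natural reading. What remains open is that neither the scale nor an interval method is named.
- **An odds ratio of 0 or infinity can be reported** with a one-sided exact bound, and the choice of an exact test points that way. Only 0 v 0 is undefined. The convention is still unwritten.
- **The Wald interval is not in the plan.** It is shown here only because the method is unnamed and the choice matters.
- **The practical effect is limited.** At equal rates, a significant omnibus result together with an event-free arm occurs in 0.3% to 2.2% of trials. The 24% depends on an assumed 1/3/6% pattern.

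A reader might also infer that a harm could be hidden. It could not: Fisher p-values are valid with zero cells, and frequencies and proportions are tabulated.

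Two nearby points do not support this finding. The rows state "The p-values will be corrected using the Benjamin- Hochberg FDR method to ensure that the family-wise Type I error remains at 0.05", although that procedure targets the false discovery rate. Some safety outcomes named in sections 2 and 5 have no row in the tables. Both are separate wording matters.

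**Conclusion.** The point holds as a minor defect in safety reporting. The omnibus odds ratio cannot be computed with the method named, in any of the ten rows and at any event rate. This part needs no assumption. The pairwise odds ratio is a poor choice for the sparse data the rows themselves expect. At 127 or 132 per arm, every significant table with up to 8 events has an event-free arm, so at least one pair gives 0, infinity or an undefined value. How often that happens depends on event rates the SAP does not give.

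The SAP does not say whether pairwise odds ratios appear after a non-significant omnibus test. If they do not, Table 2 then yields no usable effect estimate, and section 7.1 has to supply one on an unnamed scale with an unnamed interval. P-values, proportions and all efficacy results are untouched.

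**What to change.** - Delete the omnibus odds ratio from the ten safety rows and keep the omnibus p-value.
- For every safety endpoint, whatever the omnibus result, report events/n and the risk difference of each dose against placebo, with a 95% interval that is valid with zero cells (for example Newcombe or Miettinen-Nurminen). Name the scale and the method in section 7.1 or Table 2.
- If pairwise odds ratios are kept, report them with exact intervals, mark 0 v 0 as not estimable, and say whether they appear when the omnibus test is not significant.

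The cost is one reworded column, one named method and one more interval per comparison. Data collection and sample size are not affected.

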3.2. Blinding/masking

The participants, investigators, and assessors will be blinded to the randomization groups. Blinding will be accomplished by over-encapsulating each medication, making Ketotifen Fumarate and placebo capsules appear indistinguishable. TEVA Canada provided the treatment (ketotifen). Also, Bay Area Research Logistics (BARL) Hamilton, ON Canada, a company that specializes in clinical trial medication packaging and distribution, did the over encapsulation by placing the appropriate number of ketotifen tablets or lactose placebo with the methyl cellulose so that the investigational product in each treatment arm looked identical. However, unblinding might happen whenever serious suspected adverse reactions.

Alberta Health

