| Participants requiring | The analyses will be unadjusted to avoid estimates with | Odds ratio and p-value for both |
| reoperation for contracture at | wide confidence intervals since we expected that the event | the omnibus and pairwise |
| Week 12 | rate might be low and that this is likely no event in some treatment groups. | differences models. |
| | Fisher's exact test | |
| | The test will compare the proportion of participants requiring reoperation for contracture at Week 12 in the treatment groups. | |
| | If the test produces a significant p-value at α = 0.05, a post-hoc test will be performed to identify groups that differ. | |
| | The p-values will be corrected using the Benjamin- | |
| | Hochberg FDR method to ensure that the family-wise | |
| | Type I error remains at 0.05. | |

| Study Endpoint | Statistical Model | Estimate of treatment effects |
|--|--|--|
| Suspected unexpected Serious | The analyses will be unadjusted to avoid estimates with | Odds ratio and p-value for both |
| Adverse Reaction (SUSAR) up to | wide confidence intervals since we expected that the event | the omnibus and pairwise |
| Week 52 | rate might be low and that this is likely no event in some | differences models. |
| | treatment groups. | |
| | Fisher's exact test The test will compare the proportion of SUSAR up to Week 52 in the treatment groups. | |
| | If the test produces a significant p-value at α = 0.05, a post-hoc test will be performed to identify groups that differ. | |
| | The p-values will be corrected using the Benjamin- Hochberg FDR method to ensure that the family-wise Type I error remains at 0.05. | |
| Fatal or life-threatening SAE up to Week 52 | The analyses will be unadjusted to avoid estimates with wide confidence intervals since we expected that the event rate might be low and that this is likely no event in some treatment groups. | Odds ratio and p-value for both the omnibus and pairwise differences models. |
| | Fisher's exact test | |
| | The test will compare the fatal or life-threatening | |
| | SAE proportion in the treatment groups up to Week 52. | |
| | If the test produces a significant p-value at α = 0.05, a post-hoc test will be performed to identify groups that differ. | |

| Study Endpoint | Statistical Model | Estimate of treatment effects |
|---|---|--|
| | The p-values will be corrected using the Benjamin- Hochberg FDR method to ensure that the family-wise Type I error remains at 0.05. | |

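### SUSAR proportions are tested between ketotifen and placebo, but the SAP does not say that SUSAR status is fixed before unblinding (minor)

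*SAP*

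**What the plan says.** Table 1 of the SAP lists the proportion with SUSAR, to Week 12 and to Week 52, among ten safety endpoints. Table 2 (section 7.2) assigns Fisher's exact test to each. For Week 12 it states: "The test will be used to compare the proportion of SUSAR up to Week 12 in the treatment groups". For Week 52: "The test will compare the proportion of SUSAR up to Week 52 in the treatment groups". The groups are placebo and both ketotifen doses, and the output is an odds ratio and p-value for the omnibus and pairwise comparisons. Follow-up is conditional: "If the test produces a significant p-value at α = 0.05, a post-hoc test will be performed to identify groups that" differ, with Benjamini-Hochberg correction. The analyses are left unadjusted "since we expected that the event rate might be low and that this is likely no event in some treatment groups".

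Section 3.2 blinds participants, investigators and assessors, then makes an exception: "However, unblinding might happen whenever serious suspected adverse reactions".

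The SAP spells out the abbreviation SUSAR. It does not say who judges suspicion and expectedness, whether that judgement is locked before unblinding, or whether a placebo participant's event keeps its status afterwards. Fatal or life-threatening SAEs and other SAEs have their own rows, with no wording about causality.

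**The concern.** A between-arm test needs an outcome that is ascertained in the same way in every arm. On the SAP's own expansion of the term, a SUSAR is a suspected reaction, so its status depends on a causal judgement about the study drug. Every SUSAR is also a serious suspected reaction, so every SUSAR falls within the section 3.2 exception. The judgement that defines the endpoint can therefore be made or revised with the arm known, and nobody who knows that a participant took lactose would suspect ketotifen.

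If that happens, placebo events leave the numerator while comparable ketotifen events stay in it. Equal event rates can then look like harm. The other SAE row may shift the opposite way: if *other* means SAEs that are not SUSARs, a reclassified non-fatal placebo event moves into placebo's count there.

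**Working it through.** **Inputs.** The SAP gives no SUSAR rate, expected count or power for this comparison, so there is no stated figure to reproduce.

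- Arm size, from section 4: "A total sample size of 381 participants (127 participants per arm) was determined to be adequate", so 381 / 3 = 127. Later, "the sample size was increased to 395": 395 / 3 = 131.7, or 131, 132 and 132.
- Omnibus level 0.05, from Table 2.
- True event rate π, equal in all arms: assumed, 1% to 10%.
- Fraction f of placebo events not counted as SUSAR: assumed 0, 0.5 or 1.

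**Step 1: counts at which the test becomes significant.** With n per arm and counts (a, b, c), the probability of a table given its total is C(n,a)·C(n,b)·C(n,c) / C(3n, a+b+c). The p-value sums this over all tables with the same total that are no more probable than the observed one. With n = 127 and no placebo events counted:

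| Placebo, 2 mg, 5 mg | Omnibus p |
|---|---|
| 0, 1, 1 | 1.00 |
| 0, 4, 4 | 0.137 |
| 0, 5, 5 | 0.053 |
| 0, 6, 6 | 0.028 |

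With 131, 132 and 132 per arm, the last two are 0.053 and 0.029. For 0, 6, 6, each dose against placebo has p = 0.0294 and the two doses do not differ. Benjamini-Hochberg over the three pairs gives 0.0294 × 3/2 = 0.044, so the follow-up would also be significant. Six per ketotifen arm is 6/127 = 4.7%.

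**Step 2: probability of a false harm signal.** The counted placebo events are Binomial(127, π(1 − f)), and each ketotifen arm is Binomial(127, π). Sum the probability of all outcomes with omnibus p ≤ 0.05 and a placebo count below the mean of the two ketotifen counts:

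| π | Expected events per arm (127π) | f = 0 | f = 0.5 | f = 1 |
|---|---|---|---|---|
| 1% | 1.27 | 0.8% | 1.4% | 2.5% |
| 2% | 2.54 | 1.6% | 4.1% | 11.6% |
| 3% | 3.81 | 2.0% | 7.9% | 34.7% |
| 5% | 6.35 | 2.2% | 13.9% | 85.2% |
| 10% | 12.7 | 2.4% | 30.6% | 99.99% |

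With f = 0 the omnibus test rejects, in either direction, in 1.2% to 4.7% of trials over these rates. It keeps its level when all arms are classified alike.

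**Step 3: the odds ratio.** With k events on a ketotifen arm and none counted on placebo, the odds ratio is (k × 127) / ((127 − k) × 0), which is infinite for any k ≥ 1. This can also occur without bias: the chance of an empty placebo arm at f = 0 is 0.99^127 = 28% at a 1% rate, 0.98^127 = 7.7% at 2% and 0.97^127 = 2.1% at 3%. With f = 1 it is certain.

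**The case against.** A reader might infer that placebo events must drop out of the SUSAR count once the code is broken. The SAP does not say so. Section 3.2 says only that unblinding might happen, and section 5 plans to compare SUSARs in each arm, which suggests that placebo participants can have them. If suspicion and expectedness are judged blind and kept, there is no bias of this kind, as the f = 0 column shows.

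Nor is the unblinding exception aimed at SUSARs alone. It covers serious suspected reactions, expected or not, and SUSARs are a subset.

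The counts of six per ketotifen arm with none on placebo combine total loss with a rate well above what the SAP seems to expect. At 1%, even total loss gives a false signal in only 2.5% of trials. Empty arms and infinite odds ratios are a hazard of any rare endpoint, and the SAP foresees them.

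Who judges causality, and when, is commonly set in the protocol, which is not at hand. The two other SAE categories already give comparisons that do not mention causality.

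Most of this stands, and it reduces the point to a minor one. Two things remain. Choosing SUSAR as a tested endpoint is an SAP decision, and a comparison of SAEs regardless of causality is a sounder test whatever the protocol says. The existing SAE rows do not fully provide it: Table 1 separates fatal or life-threatening SAEs from other SAEs without defining *other*, while the Week 52 row labelled other SAE describes a comparison of SAEs without that restriction.

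**Conclusion.** The point holds in conditional form and is minor. The SAP tests an endpoint that depends on a causal judgement which can be made with the arm known, and it does not tie the analysis to the blinded judgement. If classification follows unblinding, the bias is towards harm. Its size depends wholly on the assumed rate and loss: at true rates of 1% to 3% the false-harm probability is 2.5% to 35% with total loss and 1.4% to 7.9% with half lost, against 0.8% to 2.0% with none. At the low rates the SAP anticipates, a false significant test is unlikely. The likelier harm is an uninterpretable odds ratio. The calculation does not show that placebo events will be reclassified, and nothing here touches the primary endpoint or the sample size.

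**What to change.** Remove the two SUSAR rows from testing in Table 2 and report SUSARs as counts or a listing by arm. In their place, test the proportion with any SAE regardless of causality, to Week 12 and to Week 52, in the safety population. This gives one comparison covering all SAEs and settles whether the tested SAE row excludes SUSARs. Align the wording of Table 1 and the Week 52 row with it.

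If a SUSAR comparison is kept, state that it uses the causality and expectedness judgement recorded before any unblinding, and that this judgement is retained for placebo participants.

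The cost is a change of SAP wording, using SAE data the SAP already plans to analyse. The downside is that SUSARs no longer carry a p-value. When to unblind is unaffected.

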The PrEvention of post-traumatic contractuRes with Ketotifen I (PERK-I) trial, a Phase II singlecenter randomized clinical trial (RCT) that compared oral Ketotifen Fumarate to a lactose placebo showed that Ketotifen Fumarate was neutral in terms of improving elbow range of motion (ROM)⁶. However, a subgroup of the trial, i.e., those who underwent surgery, indicated that Ketotifen Fumarate improved their range of motion. Therefore, the PrEvention of posttraumatic contractuRes with Ketotifen 2 (PERK-2) trial will assess the effectiveness of Ketotifen Fumarate in increasing the range of motion among surgical patients.

2. Study Objectives

The PERK-2 study aims to demonstrate that Ketotifen Fumarate (2 mg or 5 mg) administered within 10 days of injury is more effective than a placebo in reducing post-traumatic elbow joint contractures in adult participants with elbow fractures and/or dislocations. The efficacy of Ketotifen Fumarate over placebo will be assessed by comparing the difference in elbow range

Patient-Reported Outcome Measures (PROM). Lastly, the study will assess the safety of Ketotifen Fumarate through the reporting of adverse events (AE) and serious adverse events (SAE), fracture healing, and heterotopic ossification (HO) formation.

3. Study design

The PERK-2 trial is a phase III randomized controlled multicentre trial with three parallel groups. Eligible participants were assigned to receive Ketotifen Fumarate 2 mg, Ketotifen Fumarate 5 mg, or a lactose placebo in a 1:1:1 ratio. Eligible participants will be recruited at fifteen centers across North America.

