3.1. Treatment Allocation/Randomization

Randomization will be centralized, secured, and concealed via a computer-generated randomization scheme to prevent allocation bias. The randomization criteria will be reviewed and approved by an independent Biostatistician. Screening, randomization, and enrolment will be organized through the Epidemiology Coordinating and Research Centre (EPICORE) at the University of Alberta. Eligible participants will be assigned to Ketotifen Fumarate 2 mg, Ketotifen Fumarate 5 mg, or lactose placebo in a 1:1:1 ratio. A computer generated randomization scheme stratified by site with block sizes of 3:6:9 will be used to assign eligible participants. The Investigators will have access to the randomizer (on REDCap) over the Internet via a desktop computer or a web-enabled smartphone.

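### Safety rows: the Benjamini-Hochberg step is mislabelled as family-wise control, is redundant after the omnibus gate, and makes it harder to name a harmed dose

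*SAP*

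**What the plan says.** The safety rows of Table 2 (SAP section 7.2) share one template. An omnibus Fisher's exact test compares the arms. Then: "If the test produces a significant p-value at α = 0.05, a post-hoc test will be performed to identify groups that" differ. The post-hoc p-values are corrected by Benjamini-Hochberg, described as the "Hochberg FDR method to ensure that the family-wise Type I error remains at 0.05". The reported results are "Odds ratio and p-value for both the omnibus and pairwise differences models".

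The trial is a "phase III randomized controlled multicentre trial with three parallel groups", so each row has three pairwise comparisons. Table 1 (section 5) lists ten safety endpoints: five event types, each at Week 12 and again at Week 52, ending with "The proportion of participants requiring reoperation for contracture at week 52". The omnibus tests are not corrected across rows. No passage defines the family over which 0.05 is to be held.

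Section 7.1 separately plans point estimates with two-sided 95% confidence intervals for group differences, and similar analyses for the safety population. It states no multiplicity adjustment.

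**The concern.** The sentence gives a reason for the correction, and the reason does not fit. Benjamini-Hochberg is designed to limit the expected share of false findings among all findings. Family-wise error is the chance of any false finding. The two coincide in some settings and not in others, so the statement can only be judged once the family is known, and the SAP leaves it unnamed.

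The practical stake is in safety. An adjustment that raises pairwise p-values makes it harder to say which dose is associated with excess events, and the SAP itself expects these events to be rare. That price would be defensible if the step supplied an error control that was otherwise missing. The question is whether it does.

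**Working it through.** **Inputs.** From the SAP: three arms, allocation to two doses and "lactose placebo in a 1:1:1 ratio"; "A total sample size of 381 participants (127 participants per arm"); omnibus level 0.05. The total was later raised to 395, or 395/3 ≈ 132 per arm; the check uses 127. Assumed: the post-hoc test is pairwise Fisher's exact, and event rates are as shown below, since the SAP says only that they may be low.

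**Step 1: does the stated 0.05 hold within a row?** Yes. Simulating the plan as written (omnibus gate, then three Fisher tests with Benjamini-Hochberg) with equal arms and event rates of 1% to 30%, the chance of any false pairwise finding is 0.0005 to 0.034. The large-sample value is 0.044.

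**Step 2: is the correction needed for that?** With three arms, two true equalities imply the third. So either all three pairs are null, or at most one is.
- All null: a false pairwise finding requires the gate to open, so P(any false finding) ≤ P(omnibus p ≤ 0.05) ≤ 0.05.
- One null pair: P(false finding) ≤ P(that pair's Fisher p ≤ 0.05) ≤ 0.05.

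The gate with unadjusted pairwise tests therefore keeps 0.05. Simulated values with equal arms (20,000 runs each):

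| Event rate | Gate, no correction | Gate plus correction |
|---|---|---|
| 1% | 0.002 | 0.0005 |
| 2% | 0.021 | 0.006 |
| 5% | 0.039 | 0.018 |
| 10% | 0.048 | 0.025 |
| 20% | 0.046 | 0.030 |
| 30% | 0.051 | 0.034 |

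The 0.051 is within simulation error of the bound (standard error √(0.05 × 0.95/20,000) = 0.0015); a separate run gave at most 0.049. With neither gate nor correction the figure reaches 0.092.

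**Step 3: what does the correction cost?** For ordered p-values p(1) ≤ p(2) ≤ p(3), the adjusted value is the minimum over j ≥ i of 3·p(j)/j. A lone small p-value must then be at most 0.05/3 = 0.0167. Chance of flagging 5 mg against placebo, 127 per arm, 20,000 runs:

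| Assumed rates, placebo/2 mg/5 mg | Fisher alone | Gate only | Gate plus correction | Loss from correction |
|---|---|---|---|---|
| 1/1/7% | 59.7% | 59.4% | 47.9% | 11.5 points |
| 1/4/7% | 59.8% | 55.1% | 43.0% | 12.1 points |
| 2/2/10% | 71.2% | 70.2% | 61.3% | 8.9 points |

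The gate itself costs 0.3 to 4.7 points. In five further assumed settings where only 5 mg is harmful, from 1% against 5% to 10% against 25%, the correction costs about 5 to 10 points (for example 30.3% to 20.8%, and 84.9% to 80.0%).

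**Step 4: what if the family were the ten endpoints?** The omnibus tests are uncorrected, so nothing controls error there. Applying Benjamini-Hochberg across ten independent endpoints would not give family-wise control either. With 1, 3, 5 and 7 true effects (taken as always detected), the family-wise error is 0.087, 0.134, 0.141 and 0.115, while the false discovery rate stays at or below 0.05. Whether the SAP's sentence is true thus depends on the family it leaves unnamed.

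**The case against.** The strongest defence is that the sentence is correct where it stands. It sits inside each endpoint's row, directly after that row's post-hoc test, so its natural family is the three pairs of that row. If all three are null, false discovery rate and family-wise error are the same thing; if one is null, its adjusted p-value is never below its raw one. Benjamini-Hochberg alone, without the gate, keeps the error at no more than 0.034 with Fisher tests. This stands. A reader might infer from the method's name that the 0.05 is not held; within a row, it is. What remains is that gate and correction each suffice, so using both is redundant, and the correction is the costlier of the two.

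A reader might also infer that the SAP promises 0.05 over all ten safety endpoints and breaks that promise. No passage makes the promise. Nor is there a sound single figure for error over ten rows: Week 12 events are contained in Week 52 events, so the rows are not independent, and the result depends heavily on event rates the SAP does not give.

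Finally, one might conclude that harms would go unseen. The omnibus test is uncorrected and reported in every row. In the three scenarios it flags an imbalance in about 75%, 59% and 84% of trials. The loss is in naming the arm, not in raising the signal. The unadjusted intervals planned in section 7.1 soften it further.

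**Conclusion.** A minor but real flaw. The safety rows describe a false-discovery-rate method as family-wise control and name no family. On the natural reading the 0.05 is kept, but the omnibus gate already keeps it, so the correction does no work towards its stated aim. It costs about 9 to 12 percentage points in the three main scenarios, and 5 to 10 in the others examined, for identifying 5 mg as harmful against placebo.

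These sizes rest on assumed event rates, 127 per arm, and pairwise Fisher tests as the post-hoc step. The redundancy does not depend on the rates; it follows from having three arms and an omnibus gate at 0.05. Primary and secondary efficacy analyses are untouched.

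**What to change.** In all safety rows of Table 2, delete the Benjamini-Hochberg correction and the family-wise sentence, and state once that no error control is claimed across safety endpoints. Report each dose against placebo with an unadjusted exact p-value and a 95% confidence interval. Then choose one of two positions and write it down:

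- Declare safety p-values descriptive, and report the dose-against-placebo comparisons regardless of the omnibus result.
- Keep per-row family-wise control: retain the omnibus gate for any statement of significance, and use unadjusted pairwise tests after it.

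The cost is SAP wording; no data, visit or efficacy analysis changes. The downside is somewhat more nominal safety signals to interpret. Under the first position the per-row error can reach about 0.09; under the second it stays within 0.05.
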